9.3 THE FINAL EFFECTIVENESS EVALUATION

For the final effectiveness evaluation, the three items ([Improved, Unchanged, Aggravated]) evaluated at the end of the last visit will be summarized using number of subjects, percentage, 95% confidence intervals. In addition, if final effectiveness is evaluated as [Improved], it is classified as [Efficacy]. And If final effectiveness is evaluated as [Unchanged, Aggravated], it is classified as [Inefficacy].

9.4 UNIVARIATE ANALYSIS

The following categorical variables will be summarized using number of subjects, number of efficacy, efficacy rate and 95% confidence interval. Efficacy will be analyzed using Pearson's chi-square test or Fisher's exact test to determine if statistically significant differences exist. (However, if [Diabetes mellitus complications] responds with [Not applicable], [Pregnancy]

CONFIDENTIAL

STATISTICAL ANALYSIS PLAN

responds with [Not applicable], [Height] responds with [Not done], it is excluded from Pearson's chi-square test or Fisher's exact test.)

- Gender (Male, Female)
- Smoking status (Never smoked, Ex-smoked, Currently smokes)
- Family history of T2DM (Yes, No)
- Previous allergy (Yes, No)
- Diabetes mellitus complications (Retinopathy, Neuropathy, Nephropathy, Vasculopathy, Other) (Yes, No, Not applicable)
- Medical history (Yes, No)
- Comorbidities (Yes, No)
- Prior medication (Yes, No)
- Concomitant medication (Yes, No)
- Other anti-diabetic agent (Yes, No)

The following continuous variables will be summarized using number of subjects. Efficacy will be summarized using odds ratio and 95% confidence interval by using simple logistic regression.

- Age (years)
- Height (cm)
- Weight (kg)
- Duration of disease (years)
- Total period of drug use (days)
- Total number of administrations
- Average number of administration per day

Subjects of special investigation will be summarized using number of subjects, number of efficacy, efficacy rate and 95% confidence interval. Efficacy will be analyzed by using Pearson's chi-square test or Fisher's exact test to determine if statistically significant differences

CONFIDENTIAL

STATISTICAL ANALYSIS PLAN

exist.

- Geriatric population (65 years or more, Less than 65 years)
- Pregnant women (Yes, No, Not applicable)
- Renal impairment (Yes, No)
- Hepatic impairment (Yes, No)
- Long-term use (24 weeks or more)

9.5 MULTIVARIABLE ANALYSIS

As a result of simple logistic regression, statistically significant variables will be included in a multivariable logistic regression and odds ratio and 95% confidence interval will be provided per variable. (However, Variables with the Variance Inflating Factor (VIF) exceeding 10 can be excluded from the model.) The complete case analysis will be used to handle missing values of variables in the multivariate logistic regression model.

9.6 PRIMARY ENDPOINT FOR LONG-TERM EFFECTIVENESS SET

The change from baseline after 12 weeks and/or 24 weeks in HbA1c will be summarized using number of subjects, mean, SD, median, minimum, maximum, 5th percentile, 95th percentile, and will be compared using paired t-test.

9.7 SECONDARY ENDPOINTS FOR LONG-TERM EFFECTIVENESS SET

- 1) The frequency, percentage and 95% confidence interval of the changes from baseline to 12 and 24 weeks will be summarized for Long-term effectiveness set who had HbA1c reaching less than 7% (target effectiveness response rate).
- 2) The frequency, percentage and 95% confidence interval of the changes from baseline to 12 and 24 weeks will be summarized for Long-term effectiveness set whose HbA1c was decreased by at least 0.5% at the last visit (relative effectiveness response rate).
- 3) For FPG, Weight, SBP and DBP, the changes from baseline to 12 and 24 weeks will be summarized for Long-term effectiveness set using number of subjects, mean, SD, median, minimum, maximum, 5th percentile, 95th percentile, and will be compared using paired t-test.

CONFIDENTIAL

STATISTICAL ANALYSIS PLAN

4) Mean difference in the change of HbA1c according to following variables will be analyzed for Long-term effectiveness set using t-test or ANOVA (Analysis of Variance).

- Age group (Less than 19 years, 19 years or older and less than 30 years, 30 years or older and less than 40 years, 40 years or older and less than 50 years, 50 years or older and less than 60 years, 60 years or older)
- Gender (Male, Female)
- Height (<median, \geq median)
- Weight (<median, \geq median)
- Smoking status (Never smoked, Ex-smoked, Currently smokes)
- Duration of disease (<median, \geq median)
- Family history of T2DM (Yes, No)
- Previous allergy (Yes, No)
- Diabetes mellitus complications (Retinopathy, Neuropathy, Nephropathy, Vasculopathy, Other) (Yes, No, Not applicable)
- Medical history (Yes, No)
- Comorbidities (Yes, No)
- Prior medication (Yes, No)
- Concomitant medication (Yes, No)
- Other anti-diabetic agent (Yes, No)
- Geriatric population (65 years or more, Less than 65 years)
- Pregnant women (Yes, No, Not applicable)
- Renal impairment (Yes, No)
- Hepatic impairment (Yes, No)
- Total period of drug use (<median, \geq median)
- Total number of administration (<median, \geq median)
- Average number of administration per day (<median, \geq median)

CONFIDENTIAL

STATISTICAL ANALYSIS PLAN

- Reasons for early interruption (Change to other antidiabetics, Consent withdrawal, Adverse events, Patient refusal to continue taking study medication, Follow up loss, Others)

9.8 THE FINAL EFFECTIVENESS EVALUATION FOR LONG-TERM EFFECTIVENESS SET

For the final effectiveness evaluation, the three items ([Improved, Unchanged, Aggravated]) at the time of week 24 will be summarized for Long-term effectiveness set using number of subjects, percentage, 95% confidence intervals. In addition, if final effectiveness is evaluated as [Improved], it is classified as [Efficacy]. And If final effectiveness is evaluated as [Unchanged, Aggravated], it is classified as [Inefficacy].

10. APPENDIX

10.1 APPENDIX 2

Appendix 2 will be prepared for the Use Result Surveillance. The number of subjects whose CRF was retrieved, safety set, effectiveness set by year of the study will be presented. The number of subjects excluded from the safety evaluation, efficacy evaluation and their specific reasons will be presented.

10.2 APPENDIX 3

ADR collected in use result surveillance will be summarized using the number of study sites, the number of safety set, the number of subjects with ADR and cases of ADRs, proportion of the number with ADR according to the appendix format. SAEs, SADRs, Not SAEs, Not SADRs collected from use result surveillance, special study (Pharmacoepidemiology study, etc.), clinical trials and Spontaneous reporting will be coded with MedDRA and will be summarized with SOC and PT using the number of subjects and proportion of the number of subjects with AE.

CONFIDENTIAL

STATISTICAL ANALYSIS PLAN

10.3 APPENDIX 5

SAEs, SADRs, UADRs collected from use result surveillance, special study (Pharmacoepidemiology study, etc.), clinical trials and Spontaneous reporting will only be presented for Re-examination according to the format

10.4 DETAILS OF SAES LEADING TO DEATH

The details of Serious AEs leading to death collected from use result surveillance, special study (Pharmacoepidemiology study, etc.), clinical trials and Spontaneous reporting will be presented in a listing.

10.5 DETAILS OF SERIOUS UNEXPECTED AEs

The details of Serious Unexpected AEs collected from use result surveillance, special study (Pharmacoepidemiology study, etc.), clinical trials and Spontaneous reporting will be presented in a listing.

11. Changes to the planned analysis method

In the 9.7.1 demographic analysis item of Protocol (version 4.0), it is described that the administration status of this drug (average daily dose) is analyzed, but since Esglito is a composite, the average number of administrations per day will be analyzed.

[figure not shown]
12. SAS program code

The following SAS program codes will be used.

Table 6 SAS program code

Analysis method	SAS program code
Pearson's chi-square test or	PROC FREQ DATA=dataset;
Fisher's exact test	TABLE ae*factor/CHISQ EXACT; RUN;
Paired t-test	PROC UNIVARIATE DATA=dataset; VAR diff;

CONFIDENTIAL

STATISTICAL ANALYSIS PLAN

Analysis method	SAS program code
	RUN;
t-test	PROC TTEST DATA=dataset; CLASS factor; VAR chg; RUN;
ANOVA	PROC MIXED DATA=dataset; CLASS treatment; MODEL variable=treatment; LSMEANS treatment / PDIFF CL; RUN;
Simple logistic regression	PROC LOGISTIC DATA=dataset; CLASS factor; MODEL ae=factor; RUN;
Multiple logistic regression	PROC LOGISTIC DATA=dataset; CLASS factor1 factor2 factor3; MODEL ae= factor1 factor2 factor3 factor4; RUN;

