9.1.2 Dosage and Administration

The starting dose and the dose escalation schedule are based on the current authorized label in Korea.

The recommended dose is one tablet once daily as follows;

- In patients tolerating this drug 10 mg/5 mg once daily and requiring additional glycaemic control, the dose can be increased to empagliflozin 25 mg/linagliptin 5 mg once daily.
- In patients switching from separate tablets of empagliflozin and linagliptin to Esglito should receive the same dose already being taken.

The tablets can be taken with or without food, swallowed whole. If a dose is missed, it should be taken as soon as the patient remembers. If a dose is missed, and it is less than 12 hours

until the next dose, the dose should be skipped and the next dose should be taken at the usual time. A double dose should not be taken at once.

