9.7 DATA ANALYSIS

9.7.1 Analysis of Demographic Data

Demographic data and the health status of subjects for the safety evaluation will be analysed descriptively. For continuous data, mean, standard deviation, minimum value, and maximum value will be described, while for categorical data, frequency will be shown.

Parameters corresponding to demographic data are as mentioned below.

- ① Basic information and disease information
 Age, Gender, Pregnancy, Family history of T2DM, Allergy, Smoking status, Body weight, Diabetes mellitus complications (if available), Other medical history, Disease period, Elderly (Age \geq 65 years), Renal impairment and Hepatic impairment, Long term use(over 24 weeks)
- ② Medication information
 Concomitant medication, Any anti-diabetic agents, Study drug administration status (total period of drug use, average of daily dose), Reason for early interruption

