4.2 SAFETY SET

These include those who signed the data release consent form to participate in this study as subject, took Esgliteo once at least, and were followed up by the physician once or more. Reflecting MFDS guideline, the cases below shall be excluded from safety analysis set (defined below) in the following order:

CONFIDENTIAL

SD 0400 A v4.0
Statistical Analysis Plan
Protocol No.: 1275-0028

11/38 page

Effective Date: 10-Jan-2022

STATISTICAL ANALYSIS PLAN

- a. Cases not signed or signed on the data release consent form of Esgliteo post-market surveillance (PMS) prior to the contract date
- b. Cases administrated Esgliteo prior to the contract date
- c. Cases administrated Esgliteo prior to the signed on the data release consent form
- d. Not administrated an Esgliteo
- e. Follow-up failure: Patients whose safety information cannot be obtained due to follow-up loss
- f. Violation of efficacy·effectiveness, Dosage
- g. Dual registration
- h. Violation of Inclusion/Exclusion criteria

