6.3 HANDLING OF DERIVED VARIABLES

The baseline is considered to be the start date of the first administration of Esgliteo and the baseline value is defined as the last value measured before the first administration.

Derivation/imputation of variables will be performed as in the following.

Table 3 Derived variables

Variable	Derivation Method
Change from baseline	Post-baseline value – Baseline value
Age group	Less than 19 years 19 years or older and less than 30 years 30 years or older and less than 40 years 40 years or older and less than 50 years 50 years or older and less than 60 years 60 years or older
Duration of disease (years)	(Date of data release consent – Diagnosed date) / 365.25
Geriatric population	65 years or older, Less than 65 years
Total period of drug use(days)	End date of Esgliteo final administration – Start date of Esgliteo first administration+1 If [Continuing] is checked on CRF [DISPENSING OF ESLITEO] page, end date of Esgliteo final administration will be replaced with date of last safety assessment, and if date of last safety assessment is missing, it is replaced with date of last visit.
10/5mg, 25/5mg Sum of total period of drug use(days)	Sum of ((End date of Esgliteo administration - Start date of Esgliteo administration +1) per duration of visit) If [Continuing] is checked on CRF [DISPENSING OF ESLITEO] page, end date of Esgliteo final administration will be replaced with date of last safety assessment, and if date of last safety assessment is missing,

CONFIDENTIAL

STATISTICAL ANALYSIS PLAN

Variable	Derivation Method
	it is replaced with date of last visit.
Total number of administrations	Sum of (Administration frequency ^[1] ×period of drug use) per duration of visit [1] QD: Once a day, BID: Twice a day, TID: Three times a day, QID: Four times a day, PRN: Whenever necessary But, the value collected with PRN is excluded from analysis.
Average number of administrations per day	Total number of administrations / Total period of drug use
Duration of AE (Days)	AE end date – AE onset date +1 If [Continuing] is checked on CRF [ADVERSE EVENTS] page, AE end date will be replaced with date of last safety assessment, and if date of last safety assessment is missing, it is replaced with date of last visit, and will mark \geq (e.g. ≥ 15).
Onset duration of AE	AE onset date – Date of first Esglito administration
Less than 7% of HbA1c	yes: HbA1c $< 7\%$ no: HbA1c $\geq 7\%$

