7.4 ESGLITEO ADMINISTRATION STATUS

Total period of drug use, Total number of administrations, Average number of administration per day will be summarized using number of subjects, mean, SD, median, minimum, maximum, 5th percentile and 95th percentile.

In addition, the frequency and percentage of reasons for early interruption are presented when the subjects prematurely withdraw the study.

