9.2 SECONDARY ENDPOINTS

- 1) The frequency, percentage and 95% confidence interval of the changes from baseline to 12 and 24 weeks will be summarized for patients who had HbA1c reaching less than 7% (target effectiveness response rate).
- 2) The frequency, percentage and 95% confidence interval of the changes from baseline to 12 and 24 weeks will be summarized for patients whose HbA1c was decreased by at least 0.5% at the last visit (relative effectiveness response rate).
- 3) For FPG, Weight, SBP and DBP, the changes from baseline to 12 and 24 weeks will be summarized using number of subjects, mean, SD, median, minimum, maximum, 5th percentile and 95th percentile, and will be compared using paired t-test.
- 4) Mean difference in the change of HbA1c from baseline to latest value according to following variables will be analyzed using t-test or ANOVA (Analysis of Variance).
 - Age group (Less than 19 years, 19 years or older and less than 30 years, 30 years or older and less than 40 years, 40 years or older and less than 50 years, 50 years or older and less than 60 years, 60 years or older)
 - Gender (Male, Female)
 - Height (<median, \geq median)
 - Weight (<median, \geq median)
 - Smoking status (Never smoked, Ex-smoked, Currently smokes)
 - Duration of disease (<median, \geq median)
 - Family history of T2DM (Yes, No)
 - Previous allergy (Yes, No)
 - Diabetes mellitus complications (Retinopathy, Neuropathy, Nephropathy, Vasculopathy, Other) (Yes, No, Not applicable)
 - Medical history (Yes, No)

CONFIDENTIAL

STATISTICAL ANALYSIS PLAN

- Comorbidities (Yes, No)
- Prior medication (Yes, No)
- Concomitant medication (Yes, No)
- Other anti-diabetic agent (Yes, No)
- Geriatric population (65 years or more, Less than 65 years)
- Pregnant women (Yes, No, Not applicable)
- Renal impairment (Yes, No)
- Hepatic impairment (Yes, No)
- Long-term use (24 weeks or more)
- Total period of drug use (<median, \geq median)
- Total number of administration (<median, \geq median)
- Average number of administration per day (<median, \geq median)
- Reasons for early interruption (Change to other antidiabetics, Consent withdrawal, Adverse events, Patient refusal to continue taking study medication, Follow up loss, Others)

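### The SAP replaces average daily dose with a count of about 1 per day that cannot separate 10/5 mg from 25/5 mg, and no listed summary or factor analysis uses dose or strength

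*SAP*

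**What the plan says.** Protocol 9.7.1 includes among the medication parameters "Study drug administration status (total period of drug use, average of daily dose". Protocol 9.7.3 item 2 then asks for HbA1c change to be compared across the 9.7.1 parameters, and 9.7.2 item 3 asks for adverse event occurrence by demographic data.

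On the regimen, Protocol 9.1.2 states "The recommended dose is one tablet once daily as follows" and, for patients who tolerate 10/5 mg and need more glycaemic control, that "the dose can be increased to empagliflozin 25 mg/linagliptin 5 mg once daily".

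SAP 11 declares one departure from the protocol. Average daily dose is not analysed; instead, "since Esglito is a composite, the average number of administrations per day will be analyzed". SAP Table 3 defines that average as "Total number of administrations / Total period of drug use". The numerator sums frequency times days over the visit periods, with once daily counted as 1. The denominator runs from first start to last end, plus one day.

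SAP 7.4 gives the exposure summary: "Total period of drug use, Total number of administrations, Average number of administration per day will be summarized". Average and total number of administrations are also factors in four lists: as continuous covariates in 8.3.1 and 9.4, and split at the median in 9.2 item 4 and 9.7 item 4. SAP 4.2(f) excludes from the safety set "Violation of efficacy·effectiveness, Dosage", and the effectiveness and long-term sets are drawn from the safety set.

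Table 3 also derives days on 10/5 mg and days on 25/5 mg. SAP 7.4 does not name that variable, no factor list uses it, and no table title in Table 7 mentions it.

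**The concern.** The stated reason is that the product has two components. But the strengths are 10/5 and 25/5 mg, so the linagliptin dose is the same in both and a single number, empagliflozin mg/day, describes what a patient takes. A count of tablets per day does not, because both strengths are one tablet a day.

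The study title names two strengths and the protocol describes moving from one to the other. On the SAP as written, the exposure summary would not show how the cohort divides between strengths or how the mean dose varies. Neither adverse events nor HbA1c change would be examined by dose. The rows printed in their place would be a near-constant and a near-copy of treatment duration, and a reader could take them for dose results.

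**Working it through.** The plan gives no figure to reproduce on this point, and the 600 patients are a regulatory number. The check applies the Table 3 definitions directly.

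**1. The substitute against the dose, over 168 days without a gap.** Average administrations per day = (1 × 168)/168 = 1.00. Mean empagliflozin dose = (10 × d10 + 25 × d25)/(d10 + d25), where d10 and d25 are the days on each strength.

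| Days on 10/5 | Days on 25/5 | Mean empagliflozin (mg/day) | Administrations per day |
|---|---|---|---|
| 168 | 0 | 10.00 | 1.00 |
| 126 | 42 | 13.75 | 1.00 |
| 84 | 84 | (840 + 2100)/168 = 17.50 | 1.00 |
| 42 | 126 | 21.25 | 1.00 |
| 0 | 168 | 25.00 | 1.00 |

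A 2.5-fold range of dose maps to one value.

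**2. What does move the substitute.** The denominator spans a gap and the numerator does not, so a gap of g days gives (168 − g)/168: 0.98, 0.96, 0.92 and 0.83 for g = 3, 7, 14 and 28. Counting one or two boundary days twice gives 169/168 = 1.006 or 170/168 = 1.012. These are features of dates, not of dose.

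**3. Limiting case: no gaps or overlaps.** Every value is 1. A logistic model with an intercept and a constant has rank 1, so no odds ratio can be estimated. The below-median group has 0 patients, so the t-test cannot run. Total number equals total period exactly (r = 1).

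**4. Realistic cases, by simulation.** Assumptions that are not in the documents: 600 patients, 85% with 168 to 196 days of use and the rest with 30 to 167, and a given share with one gap of 1 to 14 days. Variance inflation factor (VIF) = 1/(1 − r²), with r the correlation of total number and total period.

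| Share with a gap | Patients below median of average per day | r | Median VIF | Same median half for number and period |
|---|---|---|---|---|
| 5% | about 30 | 0.9985 | about 350 | 98% |
| 20% | about 119 | 0.995 | about 99 | 93% |
| 40% | about 240 | 0.992 | about 61 | 89% |

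At 5%, the average has mean 0.998 and SD 0.014. The split then contrasts patients with a date gap against the rest.

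**5. Precision of the odds ratio.** Take one simulated sample with 5% gaps, everyone at 168 days (SD about 0.0128) and an assumed adverse event proportion of 15%. The standard error of the log odds ratio per one administration per day is about 1/√(600 × 0.15 × 0.85 × 0.0128²) ≈ 8.9. A smaller reporting unit would rescale this without adding information.

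**The case against.** The best reply is that dose is not lost. Days on each strength are derived in Table 3, with their own rule for patients still on treatment, and SAP 7.4's total period could be read to include the by-strength version. The shell for Table B9 is a separate document and may show it. The change is declared with a reason, the protocol does not define average daily dose for a two-component tablet, and no primary safety or HbA1c result depends on it.

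Much of this stands. A reader might infer that dose is nowhere described or that the deviation is concealed; the documents support neither. What they show is a derived variable that no listed summary or factor analysis takes up.

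A reader might also call the factor analyses void. That is strictly so only if no patient has a gap or overlapping dates, which the documents do not say. With gaps the analyses run, but they compare interrupted with uninterrupted use. The value of about 1 also rests on reading SAP 4.2(f) as removing patients who take more than one tablet a day. That is the likely reading, but the SAP does not define a dosage violation, and Table 3 still codes twice, three times and four times daily and as-needed use.

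Finally, a reader might infer that the VIF limit of 10 would strip both duplicates from the multivariable models. SAP 8.3.2 and 9.5 make exclusion optional, and only variables already significant in simple regression enter. An analyst would normally drop one. The rule does not reach the univariate analyses.

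**Conclusion.** The point holds as a gap in exposure reporting and factor analysis that should be fixed; it does not threaten the main safety or HbA1c results. The reason given in SAP 11 does not justify dropping dose. The replacement is 1.00 for a gap-free once-daily patient on either strength and cannot distinguish mean doses from 10 to 25 mg/day. Two uninformative variables appear in each of four factor lists (eight rows), while dose, which Protocol 9.7.3 item 2 brings in through 9.7.1, appears in none.

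The conclusion rests on once-daily use and the likely reading of SAP 4.2(f). The degree of duplication depends on the assumed gap rates, but r stays at 0.99 or above across the range tried.

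**What to change.** - In SAP 11 and Table 3, replace the substitute with average daily empagliflozin dose = (10 × days on 10/5 + 25 × days on 25/5)/(days on 10/5 + days on 25/5), using the days Table 3 already derives.
- In SAP 7.4 and Table B9, report days on each strength and this mean dose. Counts by starting strength and of dose changes are optional.
- In 8.3.1, 9.2 item 4, 9.4 and 9.7 item 4, use dose or strength in place of average number of administrations per day, and drop total number of administrations as a factor. Keep total period of drug use.
- In the two HbA1c lists, strength groups (10/5 throughout, 25/5 throughout, both) are safer than a median split. If more than half of patients stay on 10/5 mg, the median dose is 10 and the below-median group is empty again.

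The cost is one derived variable and minor rewording; Visit 1 already records dose and start date, and later visits record changes. One caution for the report: Protocol 9.1.2 ties an increase to tolerance and to the need for more glycaemic control, so associations with dose are descriptive and not causal. This concerns reporting only, not dosing.
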